6.11.2.2.2 Procedure for Reporting a Serious Adverse Event

For an SAE occurring during the period of the clinical study, regardless of whether it is related to the treatment or not, and of whether it is expected or not, the Investigator must do the following:

- 1. Take prompt and appropriate medical action, if necessary. The safety of the subject is the first priority.
- 2. Ensure that the event is classified as an SAE. Immediately inform Advanced Clinical Pharmacovigilance of the event (within 24 hours of knowledge of the event) by fax or email and discuss further actions to be taken. Email is the preferred method.

Advanced Clinical Pharmacovigilance:

[contact] (preferred method) or E-[contact]

- 3. Complete the Adverse Event Form provided in the CRF as fully as possible.
- 4. Ensure that the event is classified as an SAE in the CRF.
- 5. Print and complete the Serious Adverse Event Form available in the electronic data capture (EDC) system as PDF document. Fax or scan and send by e mail the completed form, accompanied by any other relevant information or medical records (e.g., laboratory test results) within 24 hours to Advanced Clinical Pharmacovigilance. The demographics, medical history, previous and concomitant therapies, and adverse event pages of the CRF must be completed and available for review in the EDC system at the time of the report.
- 6. Monitor and record the progress of the event until it resolves or reaches a clinically stable outcome, with or without sequelae. For follow-up evaluations, notify Advanced Clinical Pharmacovigilance of updates within 24 hours. Serious Adverse Events will be monitored until the Investigator and Sponsor agree that the event is satisfactorily resolved.

- 7. Obtain and maintain in his/her files all pertinent medical records, information, and medical judgments from colleagues who assisted in the treatment and follow-up of the subject. If necessary, contact the subject's personal physician or hospital staff to obtain further details.
- 8. Inform Advanced Clinical Pharmacovigilance of the final outcome of the event. Send a revised or updated Serious Adverse Event Form and Adverse Event Form, if appropriate.
- 9. Comply with the applicable regulatory requirement(s) related to the reporting of SAEs to the Institutional Review Board (IRB) / Independent Ethics Committee (IEC).

If there are serious, unexpected adverse drug reactions associated with the use of the study drug, the Sponsor or designee will notify the appropriate regulatory agency(ies), Ethics Committees (EC), and all participating Investigators on an expedited basis.

6.11.2.2.3 Procedure for Reporting an Adverse Event of Special Interest

For any AESI (see Section 6.11.2.1.3) occurring during the period of the clinical study, whether related to the treatment or not, and whether expected or not, the Investigator is to do the following:

- 1. Take prompt and appropriate medical action, if necessary. The safety of subjects is the first priority.
- 2. Immediately inform Advanced Clinical Pharmacovigilance of the event by fax or email and discuss further actions to be taken (Section 6.11.2.2.2).
- 3. Complete the Adverse Event Form provided in the CRF as fully as possible.
- 4. Ensure that the event is classified as an AESI in the CRF.
- 5. Print the Adverse Event form. Fax or scan and send by e mail the completed form, accompanied by any other relevant information or medical records (e.g. laboratory test results) within 24 hours to Advanced Clinical Pharmacovigilance. The demographics, medical history, previous and concomitant therapies, and adverse event pages of the CRF must be completed and available for review in the EDC system at the time of the report.
- 6. Monitor and record the progress of the event until it resolves or reaches a clinically stable outcome, with or without sequelae. For follow-up evaluations, notify Advanced Clinical Pharmacovigilance within 24 hours. AESIs will be monitored until the Investigator and Sponsor agree that the event is satisfactorily resolved.
- 7. Obtain and maintain in his/her files all pertinent medical records, information, and medical judgments from colleagues who assisted in the treatment and follow-up of the subject. If necessary, contact the subject's personal physician or hospital staff to obtain further details.
- 8. Inform Advanced Clinical Pharmacovigilance of the final outcome of the event. Send a revised or updated Adverse Event Form, if appropriate.

6.11.2.2.4 Procedures for Suspected Allergic Contact Reaction to Topical Study Medication (Re-Challenge Patch Test and Ingredient Patch Testing)

If a subject experience a suspected allergic contact reaction associated with study medication use, the following actions should be taken to characterize the event:

- Stop all study medication.
- Take a picture of the affected area and the non-affected surrounding skin
- Document the event as an Adverse Event of Special Interest, contact immediately Advanced Clinical Pharmacovigilance and report the event within 24hrs (see Section 6.11.2.2.2).
- The subject continues to be followed for scheduled study visits while awaiting the rechallenge test results.

a) Re-Challenge with Assigned Topical Study Medication

- After all signs and symptoms of AESI have resolved and after a minimum of two weeks from last dose application, perform a re-challenge test with the study drug. Scheduling on a Monday or Tuesday is ideal, as it ensures the 48-hour and 72-96 hour follow-up assessments occur on weekdays (Table 8).
- 2) Ensure the subject has not been under any treatment with corticosteroids or antihistamines of any route of administration the week before testing.
- 3) Ensure that the skin on the back has not been exposed to the sun or artificial UV sources the week before testing.
- 4) Apply an appropriate quantity of the topical study drug to fill in the cupule of the test chamber to a naïve zone on the back either the right or left side of the center line (or the inner forearm if the back cannot be tested). If no test chamber is available on site, patch test units will be provided by the Sponsor or designee. Apply an empty test chamber as a control for the re-challenge test with topical study drug (note: an empty test chamber will not be needed for ingredient testing, if such test is warranted, as the Sponsor/designee will provide one or more controls for testing). The use of semi-occlusive conditions depends on the irritant potential of the study product and the intensity of the reaction that was observed. The method to be used should be discussed with the Medical Monitor.

Choose a skin site that was not previously involved in the inflammatory skin reaction. Cover the test chamber for 48 hours with a hypoallergenic tape.

- 5) Subject should be informed about avoiding exercise, showers, application of toiletries products, etc. to keep the test system dry
- 6) After 48 hours, remove the test chamber and evaluate the site and take photos after each reading (Table 9):
 - at approximately 30 minutes after patch test removal (1st reading) and,
 - 24 to 48 hours later (i.e., 72 or 96 hours after application) (2nd reading).

- If the result of the second reading is equivocal, the Investigator or at the Sponsors request, may perform an optional 3rd reading at 96 to 120 hours later (i.e., 6 to 7 days after application of the patch).
- Pictures of each reading and the reading results should be sent to Advanced Clinical Pharmacovigilance and medical monitor.

Day Patch Test Starts	1st reading + Photographs	2nd reading + Photographs	3rd reading (optional) + Photographs
	48 hours after study product application (30 minutes after patch test removal)	72 to 96 hours after study product application (24 to 48 hours after patch test removal)	6 or 7 days after study product application (96 to 120 hours after patch removal)
If test starts on Monday :	Wednesday	Thursday or Friday	Monday
If test starts on Tuesday :	Thursday	Friday	Monday or Tuesday

Table 8 Patch Testing Readout Schedule

Refer to Table 9 for the scoring system at each readout used by the International Contact Dermatitis Research Group (ICDRG) (Spiewak, 2008).

Table 9 Grading System for Suspected Allergic Contact Reaction

Score	Morphology	Interpretation
-	No skin changes in the tested area	Negative
?	Faint, non-palpable erythema	Doubtful reaction
+	Palpable erythema (moderate edema or infiltrate), papules not present or scarce, vesicles not present	Weak positive reaction
++	Strong infiltrate, numerous papules, vesicles present	Strong positive reaction
+++	Erythema, infiltration, confluent vesicles, bullae or ulceration	Extreme positive reaction
ir	Inflammation sharply limited to the exposed area, lack of infiltrate, small petechiae, pustules, and efflorescences other than papules and vesicles	Irritant reaction
Nt		Not tested

7) At the last reading, the investigator will refer to Table 10 and provide an overall interpretation regarding a possible sensitization reaction, which is based on results using the ICDRG scale.

Table 10 Investigator Overall Conclusion of Suspected Sensitization

Sensitization Reaction		
0	Negative (absence of reaction or might be irritant reaction)	
1	Equivocal	
2	Positive	

- 8) In case of negative reaction, the subject may resume study treatment if appropriate. Otherwise, the subject should complete end of study procedures.
- 9) If the re-challenge with assigned topical study medication is positive or equivocal, notify Advanced Clinical Pharmacovigilance and medical monitor immediately. Except in specific situations, ingredient patch testing of the topical study medication will be initiated as directed by the Sponsor (with individual ingredients at different concentrations if applicable, and possibly negative and positive controls) after a minimum of an additional two weeks (but not later than 6 months) and after all signs and symptoms have resolved.
 - The Sponsor will provide a letter to the investigator with blinded results for ingredient testing, and further instructions how the subject and his/her primary care provider can determine test results, while maintaining blinding of the investigator and site staff (Appendix 14.6).

Note: Ingredient testing will follow the above process beginning with step number 4, with testing of the individual ingredients (and controls, as applicable). The Sponsor or designee will provide the necessary supplies for ingredient testing. Given the delay when ingredient testing supplies may arrive, subjects may receive treatment for their acne other than the study drug, and should stop all acne therapy a minimum of 1 week before ingredient testing.

b) In case of suspicion of immediate contact skin reaction (such as urticaria)

A case-by-case approach will be applied and the procedure to follow will be discussed with the Sponsor.

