- g. Screening may be completed over several visits, over a 28-day period. Screening and Baseline may be completed on the same day, provided the subject meets eligibility requirements and does not require a washout period. Subjects may be re-screened one time, provided the reason for re-screening is not due to atrophic scar counts, acne severity or lesion counts.
- h. If Screening and Baseline occur as separate visits, the ICF does not have to be signed again at Baseline.
- i. Week 24 visit procedures are to be performed for early termination/exit visit.
- j. These assessments exclude the nose and the middle zone of the face (approximately 2 cm). These assessments are to be performed by the same evaluator throughout the study, for a given subject. If it is not possible to use the same evaluator to follow a given subject, evaluations between the primary and subsequent evaluator should overlap (both evaluators should examine the subject together and discuss findings) for at least one prior visit. At Week 24 or Early Termination, attempts should be made to complete assessments by the same rater as Baseline, to the extent possible.
- k. For WOCBP only. Mandatory at Screening, Baseline, Week 24 and ET visits. UPT is required at other visits if no menstrual period has occurred in the preceding four weeks. For prepubertal subjects, reconfirm pre-menses status at every visit and, in case of status change, collect information on contraceptive measures and perform a UPT according to the schedule for WOCBP. Sites will provide UPT supplies (hCG sensitivity ≤25 mIU/mL).
- Study drug refers to trifarotene (CD5789) cream or trifarotene cream vehicle. First application of study drug occurs under site staff supervision, at the clinic, at the Baseline visit. Subjects are reminded not to dose that evening.
- m. Consent to facial photography for visual evidence of treatment effect is mandatory to study participation, but only applies to designated imaging centers. Consent to photographs of patch testing results (suspected contact allergic reaction) and daily video recording of IP use on electronic tablet is mandatory for all subjects to participate in the study.

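### No pregnancy test is required before a patch containing trifarotene, and an ingredient patch after study exit can fall up to roughly 5 to 6 months after required contraception has ended

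*Protocol*

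**What the plan says.** Protocol 6.11.2.2.4 describes two stages of patch testing.

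- **Re-challenge.** Once signs have resolved, and at least two weeks after the last dose, the site is told: "Apply an appropriate quantity of the topical study drug to fill in the cupule of the test chamber". Two checks come first. Step 2 reads "Ensure the subject has not been under any treatment with corticosteroids or antihistamines of any route of administration the week before testing". Step 3 rules out recent sun or artificial UV on the back.
- **Ingredient testing.** After a positive or equivocal re-challenge, step 9 has the sponsor direct testing of the individual ingredients "after a minimum of an additional two weeks (but not later than 6 months) and after all signs and symptoms have resolved". The closing Note says: "Ingredient testing will follow the above process beginning with step number 4". The letter in Appendix 14.6 shows that the active substance is among the ingredients.
- **Exit.** Step 8 allows treatment to resume after a negative result, and adds: "Otherwise, the subject should complete end of study procedures".

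The pregnancy safeguards are elsewhere. Footnote k to the schedule (Protocol 5.1.2.2) says of the urine pregnancy test, for women of childbearing potential: "Mandatory at Screening, Baseline, Week 24 and ET visits". It continues: "UPT is required at other visits if no menstrual period has occurred in the preceding four weeks". Criterion 5.2 (Protocol 5.3.2) requires abstinence or highly effective contraception during the study and for at least 1 month after the last application of study drug. Protocol 5.3.4.1 withdraws a pregnant subject and stops her study drug.

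**The concern.** The re-challenge and ingredient patches can restart exposure to a retinoid after a break, yet nothing in 6.11.2.2.4 asks whether the woman is pregnant. Because ingredient testing enters at step 4, it does not carry over even the two checks in steps 2 and 3. Patch visits are not in the schedule and are not named in footnote k.

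The time limits also do not match: the contraception tail is 1 month, while the ingredient patch may come up to 6 months later. If the woman has left the study, the sponsor can direct a patch with the active substance when she is no longer asked to use contraception and was last tested at exit. Protocol 3.2 itself ranks teratogenicity and embryotoxicity as the most serious risk of the class. What is at stake is the safety of a few subjects; efficacy results are not touched.

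**Working it through.** The plan gives no figure to reproduce, so the check is a calendar.

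**Inputs**
- Re-challenge at least 14 days after the last dose; chamber worn 48 hours; second reading 72 to 96 hours after application; optional third reading at 6 or 7 days (6.11.2.2.4 and Table 8).
- Ingredient patch at least 2 further weeks and at most 6 months later (step 9). The start of this clock is not stated.
- Contraception through the study and 1 month after the last application (criterion 5.2).

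**Assumptions.** 1 month = 30.4 days; 6 months = 6 × 30.4 = 182.4 days; re-challenge at the 14-day minimum unless stated; the duration of the study is the subject's own participation.

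**A. Exit promptly after the re-challenge** (day 0 = last facial dose)
- Re-challenge patch on day 14, off on day 14 + 2 = 16; last reading on day 14 + 3 = 17 to 14 + 7 = 21.
- Contraception ends on day 14 + 30.4 = 44.4 to 16 + 30.4 = 46.4 if the re-challenge patch counts as an application, or on day 30.4 if it does not.
- Latest ingredient patch: day 17 + 182.4 = 199.4 to 21 + 182.4 = 203.4 (clock from the last reading), or day 182.4 (clock from the last facial dose).
- Gap = latest patch − end of contraception.

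| Clock starts at | Re-challenge counts | Gap, days | Months |
|---|---|---|---|
| Last reading | Yes | 199.4 − 46.4 = 153.0 to 203.4 − 44.4 = 159.0 | 5.0 to 5.2 |
| Last reading | No | 199.4 − 30.4 = 169.0 to 203.4 − 30.4 = 173.0 | 5.6 to 5.7 |
| Last facial dose | Yes | 182.4 − 46.4 = 136.0 to 182.4 − 44.4 = 138.0 | 4.5 |
| Last facial dose | No | 182.4 − 30.4 = 152.0 | 5.0 |

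With a later re-challenge she is still followed until its result, so required contraception cannot end before the last reading. With the clock starting there, the gap is then at most 182.4 days, or 6.0 months.

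The earliest ingredient patch is the last reading + 14, which is day 31 to 35. If the re-challenge counts, 44.4 − 35 = 9.4 to 46.4 − 31 = 15.4 days of cover remain, so there is no gap. If it does not count, the gap is 31 − 30.4 = 0.6 to 35 − 30.4 = 4.6 days.

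**B. Follow-up to Week 24** (day 1 = Baseline, Week 24 = day 169; re-challenge counted, clock from the second reading). The reading is on last dose + 17. Contraception ends at the later of day 169 and last dose + 16 + 30.4.

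| Last facial dose | Reading | Latest patch | Contraception ends | Gap |
|---|---|---|---|---|
| Week 2, day 15 | 32 | 214.4 | 169 | 45.4 days, 1.5 months |
| Week 12, day 85 | 102 | 284.4 | 169 | 115.4 days, 3.8 months |
| Week 20, day 141 | 158 | 340.4 | 187.4 | 153.0 days, 5.0 months |

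An ingredient patch placed while she is still participating has no contraception gap.

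**Age of the last test.** In case A the exit test is done at about the last reading. A patch at the 6-month limit therefore relies on a test about 182 days old.

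**The case against.** The strongest reply is that the safeguards outside this section do much of the work.

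- Footnote k does not limit its conditional test to scheduled visits. Criterion 5.1 obtains agreement to testing as required. Protocol 5.5.2 allows any scheduled procedure at an unscheduled visit. Protocol 5.3.4.1 tells subjects to have a known or suspected pregnancy confirmed and reported. All of this stands, but none of it requires a test before a patch or detects an unsuspected pregnancy.
- The re-challenge is normally done during participation, with contraception still in force. The study drug patched could also be vehicle, since the protocol does not say which side's product is used. This stands, and it is why the material gap is limited to the ingredient patch after exit.
- Step 8 does not say whether exit comes before ingredient testing, and 5.3.4 encourages women who stop study drug to keep attending. This also stands. Two details point towards exit first without settling it: the Note allows other acne treatment while supplies are awaited, which Table 4 prohibits during the study, and the Appendix 14.6 letter speaks of participation in the past tense.
- Protocol 11 defines the end of the study as the last subject's last visit. If criterion 5.2 is read that way, much of the calculated gap could disappear. Protocol 5.5 describes each subject's participation separately, and I take that as the likelier meaning, but the text does not exclude the other.
- Ingredient testing is directed by the sponsor and has exceptions. Those directions are not shown and might include a pregnancy check.

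**Conclusion.** The omission is real and minor. No pregnancy test is required before a patch containing trifarotene. For a woman of childbearing potential who has exited after a positive or equivocal re-challenge, the ingredient patch may fall from no gap up to roughly 5 to 6 months after required contraception has ended. The upper end assumes the latest permitted patch and subject-level study duration. The rest depends on when she exits, where the 6-month clock starts and whether the re-challenge patch counts as an application.

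A reader might infer that every patch test lies outside the protocol's pregnancy safeguards. The documents do not support that: during participation, contraception and the conditional test still apply, and study drug stops once pregnancy is known. A reader might also infer a gap of several months for every woman with a non-negative re-challenge. It can be nil if she is still participating, or if she is tested early and the re-challenge counts.

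Nor is a material fetal risk shown. The exposure is one test chamber, and Protocol 3.2 gives a teratogenicity margin of 98 for the cream. That margin does not strictly describe an ingredient patch, because step 9 allows other concentrations. The documents give no frequency for these reactions; I take them to be rare. No endpoint or analysis is affected.

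**What to change.** In 6.11.2.2.4, add a step before any patch that contains study drug or active substance: for women of childbearing potential, a negative urine pregnancy test immediately before application. Reword the Note on ingredient testing so that this step applies there too, and add these patch visits to the mandatory tests in footnote k. For an ingredient patch after exit, also require abstinence or highly effective contraception to be confirmed before the patch and continued for 1 month after it.

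The cost is one urine test per patch, and footnote k already says "Sites will provide UPT supplies". For the few women tested after exit there is also a contraception commitment of about one to two months: the month afterwards, plus up to a month beforehand if the lead-in in criterion 5.2 is applied. The consent form needs matching wording.

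If the sponsor's directions for ingredient testing already contain such a check, moving it into the protocol is enough for that stage.

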6.11.2.2.5 Procedures for Reporting Pregnancies

Any pregnancy occurring during clinical studies, where the fetus could have been exposed to the study drug, must be monitored until its outcome in order to ensure the complete collection of safety data.

If a subject becomes pregnant, the Investigator is to do the following:

1. Immediately inform Advanced Clinical Pharmacovigilance of the event by fax or email (Section 6.11.2.2.2).

2. Withdraw the subject from the clinical study.

- 3. Complete the Pregnancy Surveillance Form Part I: History and Start of Pregnancy, provided by the Clinical Research Associate (CRA) at the beginning of the clinical study, as fully as possible. Inform Advanced Clinical Pharmacovigilance of the pregnancy by sending this pregnancy form along with the Exit Form within 24 hours to Advanced Clinical Pharmacovigilance (see Section 6.11.2.2.2).
- 4. Monitor and record the progress of the pregnancy until its outcome. Contact the subject's regular physician (general practitioner or gynecologist) or hospital staff to obtain further details and ask for regular follow-up information.
- 5. Inform Advanced Clinical Pharmacovigilance of the progress by tri-monthly updates until the final outcome of the pregnancy, within 24 hours of receiving updates. If the subject can no longer be reached (lost to follow-up), documentation of the non-response/contact with two telephone calls and a letter (certified with return receipt) is required.
- 6. At the outcome of the pregnancy, complete the Pregnancy Surveillance Form Part II: Course and Outcome of Pregnancy, as fully as possible. Send this pregnancy form to Advanced Clinical Pharmacovigilance within 24 hours (see Section 6.11.2.2.2).
- 7. If the pregnancy leads to an abortion (voluntary, spontaneous or therapeutic), in-utero death, or congenital anomaly, follow the procedure for reporting an SAE (see Section 6.11.2.2.2).

